#### 8.3.1 Treatment completion hypothesis

Patients in the DOT arm will have higher treatment completion rate compared to the PN arm.

### 8.3.2 Statistical Model

All statistical procedures and models applied to the analysis of SVR detailed above will also be applied except for the missing data imputation which is unnecessary. All of ITT, mITT, and PP samples will be analyzed.

### 8.3.3 Power analysis

We hypothesize that patients in the DOT arm will have higher treatment completion rate, compared to the PN arm, which is expected to have 80% completion rate. Like SVR rates, we will be able to detect a minimum of 9% difference in completion rates between the two arms (i.e., 89% vs. 80%, OR=2.1) with the planned mITT sample size of N=100 in each study arm.

## 8.4 Treatment adherence

The primary data source for the treatment adherence will be the electronic blister-pack data. Blister-pack daily adherence dose will be converted to weekly (or biweekly) adherences rate in percentages, i.e., how many daily intakes per week (or per two weeks). This weekly or bi-weekly rate will be the primary data to be analyzed for testing significance of difference in repeatedly-measured adherence between the two study arms during the treatment period. Self-reported adherence will also be analyzed as a secondary analysis.

### 8.4.1 Treatment adherence hypothesis

Participants in the DOT arm will have higher blister-pack daily-dose weekly adherence rate, compared to the PN arm.

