### 3 Study Objectives

#### 3.1 Primary Objective

To determine whether SVR-12 rates are higher among those randomized to mDOT compared to those randomized to PN, among PWID treated for HCV at OTPs and community health centers.

#### 3.2 Secondary Objective 1

To examine the following outcomes overall and by randomization arm (mDOT compared to PN) among PWID treated at OTPs and community health centers:

- (i) Treatment initiation: whether a higher proportion of participants in the PN arm initiate treatment compared to mDOT arm;
- (ii) Adherence ( $\geq 80\%$  of prescribed medication taken): whether a higher proportion of those in the mDOT arm are adherent compared to PN arm;
- (iii) Treatment completion (finishing 100% of prescribed 12-week course): whether a higher proportion of participants in the mDOT arm complete treatment compared to PN arm;
- (iv) Drug resistance: whether the proportion who develop drug resistance is higher in the PN arm compared to mDOT arm;
- (v) Reinfection: whether (a) rate (incidence), and the (b) proportion who become reinfected with HCV is higher in the PN arm compared to mDOT arm;

Comparisons will be performed to determine the proportion of subjects in each arm who: a) initiate treatment; b) adhere to antiviral treatment; c) complete antiviral treatment; d) attain SVR (cure); e) develop drug resistance; f) reinfection. We will also conduct time to event analyses to examine drug resistance and reinfection outcomes. Subgroup analyses will be performed to assess differences in outcomes among those randomized to PN vs. mDOT in specific sub-populations.

#### 3.3 Secondary Objective 2

To examine factors associated with key study outcomes (treatment initiation, adherence, SVR, drug resistance and HCV reinfection) using quantitative and qualitative methods.

Quantitative methods: We will examine associations between psychosocial factors such as homelessness, co-morbid mental illness, poor social support, and high

levels of shame and stigma, with key study outcomes described above. It is hypothesized that these psychosocial variables are associated with lower rates of adherence and SVR in the PN arm, but not the mDOT arm; and associated with lower rates of treatment initiation in the mDOT arm, but not the PN arm.

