### Statistical Model

Multivariable logistic regressions will be applied to test the overall effectiveness of mDOT or PN on the five binary outcomes (success vs. failure) with the SVR rate as the primary outcome. The arm indicator will be the predictor for each outcome. With respect to adherence outcome in particular, repeatedly measured adherence will be analyzed (using 6 post-baseline time points and adherence as a continuous measure) applying a mixed effects linear model to test if the two arms are significantly different. This model accounts for within-subject longitudinal outcome correlation by taking the subject-level intercept as random. All models will include potential confounding variables that are significantly different between the two arms; the sites will be included as a covariate as well. Likewise, mixed effects logistic regression will also be applied to test the significance of PN and DOT on repeatedly-measured undetectable HCV VL throughout the intervention period, adjusting for substance use in addition to other confounding variables. Changes in illicit drug use will be analyzed using urine toxicology data from each visit, counting the “person-month” as a unit of analysis, and analyzing the percentage of person-months that are positive for use of illicit drugs during the study period using a t-test or Mann-Whitney test.

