### **Power analysis: Minimally detectable effect sizes**

**SVR:** Considering the base 80% SVR rate of in PN arm, a minimum of 9% difference between the two arms will be detected (i.e., 89% vs. 80%, Odds Ratio (OR)=2.1) in a multivariable logistic regression model in which confounding variables will explain 10% of variation in the predictor variable. This study posits that a >9% difference in SVR between the PN and mDOT groups will be clinically significant based on studies that showed that SVR in treatment naive patients was >90% [14].

Mixed effects logistic regression models for the undetectable HCV load will be able to detect even smaller percent point difference since they will utilize repeated measures for each subject no matter how large within-subject outcome correlations will be.

**Treatment initiation rate:** With anticipated 60% treatment initiation rate in the mDOT arm, a minimum of 7% difference will be detectable (i.e., 60% vs. 67%, OR=0.74) in any outcome in a multivariable logistic regression model in which confounding variables will explain 10% of variation in the predictor variable. Note that sample size for this analysis will be N=1000, the total number of randomized participants.

**Adherence rate:** With expected 80% adherence rate in the PN arm, a minimum of 9% difference in adherence rates between the 2 arms will be detectable (i.e., 89% vs. 80%, OR=2.1) in a multivariable logistic regression model. Per the repeatedly measured continuous adherence percentage outcome, mixed effects linear models will be able to detect standardized effect sizes (mean difference divided by a pooled Standard

Deviation (SD)) greater than 0.2 irrespective of magnitudes of within-subject outcome correlations over time. In a previous DOT study, a standardized effect size of mDOT vs. TAU was estimated to be 0.6.

**Treatment completion rate.** Under the expected 80% completion rate in the PN arm, a minimum of 9% difference in completion rates between the two arms will be detectable (i.e., 89% (mDOT) vs. 80% (PN), OR=2.1).

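### SAP 8.4 keeps the protocol's continuous adherence analysis but omits the at-least-80% responder analysis that answers secondary objective 3.2(ii)

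*SAP*

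**What the plan says.** **Protocol.** Objective 3.2(ii) sets the threshold at 80% or more of prescribed medication taken and asks "whether a higher proportion of those in the mDOT arm are adherent compared to PN arm". Section 4 repeats the 80% threshold for optimal adherence. Section 11.10 then gives adherence two analyses, each with its own power statement.

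- Responder analysis: "Multivariable logistic regressions will be applied to test the overall effectiveness of mDOT or PN on the five binary outcomes". Its power statement reads "With expected 80% adherence rate in the PN arm, a minimum of 9% difference in adherence rates between the 2 arms will be detectable", worked out as "i.e., 89% vs. 80%, OR=2.1) in a multivariable logistic regression model".
- Continuous analysis: "repeatedly measured adherence will be analyzed (using 6 post-baseline time points and adherence as a continuous measure", in a mixed effects linear model with a random subject intercept. It is powered for standardized effects above 0.2.

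**SAP.** Section 8.4 converts blister-pack data to a weekly or biweekly percentage and makes that the primary adherence data. The hypothesis in 8.4.1 is "Participants in the DOT arm will have higher blister-pack daily-dose weekly adherence rate, compared to the PN arm". Section 8.4.2 specifies only a mixed-effects linear model, adjusted for site, clinic type and cirrhosis, for the mITT and PP samples. Section 8.4.3 carries over the 0.2 standardized effect. Self-reported adherence is the only other adherence analysis mentioned.

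**The concern.** The objective asks about a proportion; the SAP tests a mean. The two need not move together. A gain among people already well above 80% raises the mean and leaves the proportion where it was. A small gain that carries people across the threshold does the reverse. An analyst who follows the SAP as written will finish without an answer to objective 3.2(ii).

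The protocol's own background (2.2) shows that the choice of summary can matter. For its pilot randomized trial of mDOT (n=80) it reports mean pill-count adherence of 88% versus 77% (p=0.02), and 81% versus 53% reaching 80% adherence (p=0.09). Both favour mDOT, but as printed they fall on opposite sides of 0.05.

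At stake is one stated secondary objective in an unblinded trial. The primary SVR analysis does not depend on it.

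**Working it through.** **1. Does any SAP section restore the responder analysis?**

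| Element | Protocol 3.2(ii), 4 and 11.10 | SAP 8.4 to 8.4.3 |
|---|---|---|
| Proportion taking at least 80% | Defined | Absent |
| Logistic model for it | Planned | Absent |
| 89% vs 80% power claim | Stated | Absent for adherence |
| Continuous repeated measure, mixed linear model | Planned | Kept |
| Standardized effect above 0.2 | Stated | Kept |

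Three possible rescues fail.

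- *Cross-reference.* SAP 8.2.1 (initiation) and 8.3.2 (completion) import the SVR procedures and models. SAP 8.4.2 does not.
- *The 80% completion outcome in SAP 8.3.* It requires 68 days between the start and end dates. It measures duration, and the main completion outcome in the same section expressly disregards adherence.
- *Overall adherence in SAP 5.3.1.* It appears as a predictor in the imputation model but is not defined, dichotomised or compared between arms.

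**2. Reproduce the protocol's 9-point figure.**

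Inputs:
- p1 = 0.80 and p2 = 0.89 (Protocol 11.10).
- 270 per arm after 10% attrition, two-sided 0.05, target power 80% (Protocol 11.4).
- Equal allocation (Protocol 5.4).

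Formula: z = [d√n − 1.960·√(2p̄q̄)] / √(p1q1 + p2q2), and power = Φ(z).

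- d = 0.09, p̄ = 0.845, q̄ = 0.155.
- 1.960·√(2 × 0.845 × 0.155) = 1.0031.
- √(0.1600 + 0.0979) = 0.5078.
- n = 270: (0.09 × 16.432 − 1.0031) / 0.5078 = 0.937, power **82.6%**. The detectable difference at 80% power is 8.7 points.
- A Wald test on the log odds ratio gives 81.4%.

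For SVR and initiation the protocol also assumes that "confounding variables will explain 10% of variation in the predictor variable". It does not repeat this for adherence, so applying it here is an assumption. The effective n is then 270 × 0.9 = 243, z = (1.4030 − 1.0031) / 0.5078 = 0.787, power **78.4%**, and the detectable difference is 9.2 points.

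The claim of about 9 points reproduces. The exact odds ratio is (0.89/0.11) / (0.80/0.20) = 2.02, against 2.1 as stated.

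**3. Power if the analysis is restored at the SAP's planned size** (300 per arm in the mITT sample, SAP 5.5).

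- Unadjusted: z = (0.09 × 17.321 − 1.0031) / 0.5078 = 1.094, power **86.3%**, detectable difference 8.3 points.
- R² of 10%: effective n = 270, power **82.6%**, detectable difference 8.7 points.

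**4. How much weight the pilot bears.** Suppose all 80 were analysed at 40 per arm. Then 81% versus 53% gives z = 0.28 / √(2 × 0.67 × 0.33 / 40) = 2.66, or p of about 0.008. The printed 0.09 would need about 16 per arm, since 2 × 0.67 × 0.33 × (1.695/0.28)² = 16.2. The protocol does not give the number analysed, so either a subset was used or the p-value is misprinted. The pilot is an illustration only; the finding rests on step 1.

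**The case against.** The best reply is that SAP 8.4.2 invents nothing. Protocol 11.10 singles out adherence for the continuous mixed model and powers it. That stands: the SAP omits one of two planned analyses and retains the other unchanged in kind. It also stands that only the 9-point power claim is left without an analysis.

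A second reply is that the 80% threshold is explicit only in Protocol 3.2(ii) and 4. The hypothesis in 11.3 speaks of an adherence rate expected to be 80% in the PN arm and names no cut-off, and 11.10 does not restate one. That is fair, but the odds ratio and the logistic model in 11.10 make sense only for a binary outcome, and 3.2(ii) supplies its definition.

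A third is that the SAP says it concentrates on SVR and covers only several of the secondary outcomes. It has no analysis section for resistance or reinfection either, so silence need not withdraw the protocol's logistic model. This softens the point without closing it. The SAP does cover adherence, and there it states a hypothesis, a model and a power claim that all exclude the responder outcome.

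A reader might infer outcome switching. The documents do not support that. The retained analysis was in the protocol, the outcome is secondary, SAP 1 places approval before main outcome collection and cleaning were complete, and nothing indicates that results guided the choice.

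Finally, pack data alone cannot supply the responder variable. Under Protocol 7.3, observed OTP doses are timed in the mDOT log, and the take-home packs cover 1–2 doses a week. Under 6.1.1 and 6.1.2, rescue doses sit in a separate container, and some CHC doses leave the pack early in a pill case. This objection stands in full and shapes the fix.

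**Conclusion.** The point holds as an omission that should be corrected. Objective 3.2(ii) and its 89% versus 80% power claim have no matching analysis in the SAP, and no reason is given. It goes beyond missing detail, because following the SAP tests a different quantity from the one the objective names.

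The size is one secondary objective left unanswered. No bias in the SVR comparison follows, and the protocol's 9-point figure is not in error. Power for the restored analysis is about 83% to 86% at 300 per arm. That rests on the protocol's 80% PN rate, a 9-point difference, full data on 300 per arm and, at the lower end, a borrowed R² of 10%. With 10% attrition (270 per arm) it is about 78% to 83%.

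Protocol 11.10 does not rank its two analyses, so there is no ground for calling the continuous one inferior. The case for the responder analysis is that it alone answers the objective as worded.

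**What to change.** Add to SAP 8.4:

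1. **Outcome.** Overall adherence of at least 80%, yes or no, in the mITT sample, named as the analysis that answers Protocol 3.2(ii), with the 8.4.1 hypothesis extended to match.
2. **Derivation.** Doses taken over doses prescribed, combining blister-pack data, the mDOT dose log and miDOT records, and counting recorded rescue and pill-case doses. State one rule for unreturned packs and apply it to both arms.
3. **Model.** The SAP 5.4 logistic model with the randomization stratification factors, reported as an odds ratio with its 95% confidence interval.
4. **Power.** Restate the 89% versus 80% claim at 300 per arm.
5. **Other analysis.** Keep the weekly or biweekly mixed model as the second protocol-planned analysis.
6. **Consistency.** Use the same variable for overall adherence in SAP 5.3.1, which currently lacks a definition.

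If the team prefers not to restore the analysis, the SAP should say so and give the reason, and objective 3.2(ii) should be amended to match.

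The cost is a short SAP addition and a modest amount of derivation work to merge the dose records. No further participants, visits or procedures are needed.

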### 8.4.2 Statistical Model

Mixed-effects linear model with the study as the primary predictor will be applied to the analysis of the blister-pack adherence data adjusting for the randomization stratification variables: sites, clinic types and cirrhosis status. This analysis will be applied to mITT and PP sample but not to ITT sample.

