## 11.4 Sample Size Determination

Sample size N=300 per arm, or a total of N=600, was determined based on feasibility of recruitment from all sites during the study period. Power analysis for each hypothesis below is conservatively conducted based on a reduced sample size (N= 270 per arm, or N=540 in total) after considering 10% attrition rates. The target power is 80% with a two-sided significance level of 0.05. To this end, minimally detectable effect sizes and widths of 95% confidence intervals were computed with those parameters and the sample size after attrition.

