### 3.3 Per protocol analytic sample

This per protocol (PP) analytic sample includes the enrolled study participants who 1) were randomized; 2) initiated treatment; 3) complied with the randomly assigned models of care without cross over any time during the 12-week treatment; and 4) had SVR outcome data (yes vs. no). This sample is referred to as the per-protocol (PP) analytic sample. The PP sample will be a subset of the mITT sample which is in turn a subset of the ITT sample.

The intention-to-treat principle reflects the principle that once the intervention was randomly assigned to a participant, the participant's intervention assignment will not change in the analysis even if s/he crossed over the other intervention during the trial period or did not complete intervention activities. The application of this ITT principle reflects the real-world goal of the HERO study which is to treat all PWID with HCV (i.e., all randomized individuals).

However, as the HERO study was designed as of a pragmatic randomized clinical trial (RCT), the ITT sample will not be used as the primary analytic sample because the outcomes are defined conditions on the initiation. Furthermore, the primary (SVR) and several of the other secondary outcomes (treatment completion, adherence) are only relevant among those who initiated treatment.

**All statistical analyses proposed in the present SAP will be repeated for each analytic sample.** Comparison across the three analytic samples will be compared to assess internal or external validities or limitations of the study findings. In particular, analysis of the secondary ITT sample will provide estimates of milestones along the HCV cascade of care by study arm and in the full sample. All statistical analyses will be conducted using SAS v9.4 and R 3.5 or higher, and a two-tailed significance level of 0.05 will be applied to all testing and confidence intervals.

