#### 5.4 Statistical Model

Multivariable logistic regression will be applied to test the overall effectiveness of DOT or PN on the SVR (success vs. failure) as the primary outcome. The arm indicator will serve as the primary predictor. The CONSORT and ICH-9 statistical analysis guidelines suggest that, any baseline characteristics, even if significantly unbalanced between arms, should not be included in the multivariable logistic model since baseline imbalance could be due to chance rather than systematic bias in randomized studies but include as the covariates the randomization stratification variables. In the HERO study, they are: site/city, clinic type (OAT and CHC) and stage of liver disease (cirrhosis vs no).

The primary mITT sample, nonetheless, might no longer represent a randomized pool of participants since the characteristics of participants who initiated treatments may be unequal between the two models of care which may have differential effects on triggering treatment initiations due to difference in modalities of treatment initiation and delivery. Therefore, there could exist baseline characteristics that are unbalanced beyond chance among initiated participants between the two arms. We will declare imbalance if a baseline characteristic is significantly different between the two arms with a two-sided p-value < 0.01 considering the multiplicity of testing. As such, we will include unbalanced baseline characteristics for adjusting purposes in multivariable models in addition to the randomization stratification variables, resulting in the following model:

$$\text{Logit}(P(\text{SVR})) = b_0 + b_1 * \text{TRT} + b_2 * \text{Site1} + \dots + b_8 * \text{Site7} + b_9 * \text{Clinic\_Type} + b_{10} * \text{Cirrhosis}$$

+ Unbalanced Covariates

We will consider exploring other methods to adjust potential imbalance using propensity scores or inverse probability weighting.

For the analysis of the secondary ITT sample, we will only include the randomization stratification variables following the CONSORT and ICH-9 statistical analysis guidelines since the ITT samples are purely randomized participants, resulting in the following model:

$$\text{Logit}(P(\text{SVR})) = b_0 + b_1 * \text{TRT} + b_2 * \text{Site1} + \dots + b_8 * \text{Site7} + b_9 * \text{Clinic\_Type} + b_{10} * \text{Cirrhosis}$$

For the analysis of PP model the approach applied to the analysis of the mITT sample will be applied.

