### 5.5 Power analysis

The HERO study was planned to recruit N=300 participants in each arm in the mITT sample. Considering the base 80% SVR rate in the PN arm, a minimum difference of 9% between the two arms will be detected (i.e., 89% vs. 80%, OR=2.1) with the planned sample size in a multivariable logistic regression model in which adjusting variables explain 10% of variation in the predictor variable. This study posits that a >9% difference in SVR between the PN and DOT groups will be clinically significant based on studies that showed that SVR in treatment naive patients was >90%.

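### SAP 8.4.2 adjusts the mITT and PP adherence models for randomisation strata only, without the imbalance adjustment that SAP 5.4 and Protocol 11.10 call for, so selection into treatment may confound the comparison

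*SAP*

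**What the plan says.** SAP 8.4.2 specifies a mixed-effects linear model for blister-pack adherence, "adjusting for the randomization stratification variables: sites, clinic types and cirrhosis status". It applies to the mITT and PP samples and not to ITT. SAP 8.4 adds self-reported adherence as a secondary analysis, and 8.4.2 gives no separate model for it.

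SAP 5.4 treats the same samples differently for SVR. It reasons that the two care models may trigger initiation differently, so that initiators may differ between arms beyond chance. It declares imbalance at a two-sided p<0.01 and says "we will include unbalanced baseline characteristics for adjusting purposes in multivariable models in addition to the randomization stratification variables". PP follows the mITT approach. Strata-only adjustment is kept for ITT, on the ground that ITT is the purely randomised sample. SAP 5.4 also mentions exploring propensity scores or inverse probability weighting.

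SAP 8.3.2 imports this for treatment completion: "All statistical procedures and models applied to the analysis of SVR detailed above will also be applied except for the missing data imputation". SAP 8.4.2 contains no such import.

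Protocol 11.10 (Statistical Model), in the paragraph that sets out the adherence mixed model, says: "All models will include potential confounding variables that are significantly different between the two arms".

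**The concern.** The SAP names a threat to the mITT sample, adopts a remedy for SVR and completion, and then writes an adherence model for the same sample without it. Strata-only adjustment, which SAP 5.4 reserves for the randomised sample, is applied here only to the samples it says may not be randomised.

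Differential initiation is one of the trial's own hypotheses: SAP 8.2 expects more initiation under PN. If the participants who start under DOT are more stable (or less stable) than those who start under PN, part of the adherence difference reflects who started rather than the care model. Adherence is a named secondary outcome with a directional hypothesis favouring DOT. SAP 3.3 fixes the level of the test: "a two-tailed significance level of 0.05 will be applied to all testing and confidence intervals". A bias in the arm contrast would move the true error rate away from that level.

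**Working it through.** **Inputs from the documents.** Planned size: "The HERO study was planned to recruit N=300 participants in each arm in the mITT sample". Protocol 11.4 allows for 10% attrition ("N= 270 per arm, or N=540 in total") and states "The target power is 80% with a two-sided significance level of 0.05". SAP 8.4.3 gives a detectable adherence effect of 0.2 SD. Initiation contrasts, both stated as detectable differences, are 60% versus 67% (Protocol 11.10) and 60% versus 72% (SAP 8.2.2).

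**Assumed, because the documents give no value.** Within-subject correlation ρ of 0.5 to 0.8; 12 weekly measures; the correlation of a baseline factor with adherence; the form of selection into treatment.

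**1. The plan's own figure.** Detectable effect = (1.960+0.842)·√(2/n)·√((1+11ρ)/12). At n=300 this is 0.168 SD (ρ=0.5), 0.195 SD (ρ=0.7) and 0.229 SD (ρ=1). So 0.2 SD is met up to ρ of about 0.74, not for every correlation. That is a separate matter; 0.2 SD serves here only as a yardstick.

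**2. Bias from one covariate just at the SAP threshold.**
- Imbalance at p=0.01: 2.576·√(2/300) = 0.210 SD.
- Bias: 0.210·r, which is 0.042 SD at r=0.2 and 0.084 SD at r=0.4, or 21% to 42% of 0.2 SD.
- SE of the arm effect: √(2/300)·√((1+11ρ)/12) = 0.060 (ρ=0.5) or 0.074 (ρ=0.8).
- Type I error: P(|Z + bias/SE| > 1.96).

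| r | ρ | bias/SE | Type I error |
|---|---|---|---|
| 0.2 | 0.8 | 0.57 | 8.8% |
| 0.2 | 0.5 | 0.70 | 10.8% |
| 0.4 | 0.8 | 1.14 | 20.7% |
| 0.4 | 0.5 | 1.40 | 28.8% |

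This is conditional on such a covariate existing. It does not say how likely that is.

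**3. Bias implied by the initiation rates, same mechanism in both arms.** Under a probit initiation model, the mean of a baseline factor among initiators is r·φ(z_p)/p. The ratio φ(z_p)/p is 0.644 at 60%, 0.541 at 67% and 0.468 at 72%. The between-arm differences are 0.103 and 0.176. Bias = r²·difference, taking the factor's correlations with initiation and with adherence as equal. Type I error is at n=300, ρ=0.5.

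| r | 60% vs 67%: bias (SD), error | 60% vs 72%: bias (SD), error |
|---|---|---|
| 0.3 | 0.009, 5.3% | 0.016, 5.8% |
| 0.5 | 0.026, 7.1% | 0.044, 11.4% |
| 0.7 | 0.051, 13% | 0.086, 30% |

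If what favours initiation also favours adherence, this bias favours DOT, because the arm with lower initiation is the more selected one. If the factor operates in DOT only, the bias is 0.644·r², which is 0.058 SD at r=0.3 and 0.161 SD at r=0.5.

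**4. Simulation with no true arm effect.** 500 randomised per arm, 60% versus 67% initiating, logistic selection on one covariate with log-odds slope 0.4 to 0.8, covariate–adherence correlation 0.2 to 0.4, ρ of 0.5 to 0.8.
- Same selection in both arms: the model without the covariate rejects 4.5% to 6.3% of the time.
- Selection in DOT only: it rejects from 7% up to 31% or 49%, depending on how the outcome is scaled.
- DOT only, covariate added when flagged at p<0.01: 5% to 9%.

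**5. What the p<0.01 screen catches.** With the same mechanism in both arms it flags the covariate 1% to 3% of the time in the simulation, and 2% to 14% under the model of step 3. With DOT-only selection at slope 0.4 it flags about 26% and leaves rejection as high as 9.4%; always adjusting gives about 5%.

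**6. Precision cost.** If the added covariates explain 10% of the variation in arm, n becomes 300·0.9 = 270. At ρ=0.5 the detectable effect moves from 0.168 to 2.802·√(2/270)·√(6.5/12) = 0.178 SD.

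**The case against.** Several points on the other side stand.

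- A reader might infer that confounding is shown and that the test exceeds 5%. The documents do not support that. SAP 5.4 speaks only of what might or could occur, and step 4 shows near-nominal error when both arms select alike at 60% versus 67%. The large figures need DOT-only selection or strong correlations, and neither document says that PN initiation is non-selective.
- A reader might infer that adherence is the only mITT analysis without the extra covariates. It is not: SAP 6.2 openly leaves them out of the subgroup models, with a reason. The point holds for outcome models.
- A reader might infer a deliberate withdrawal of the protocol rule. SAP 8.4.2 does not say that no other covariates will be used, and SAP 1 says the plan focuses mainly on SVR. An incomplete sentence is the fairer reading. Even so, the section lists its covariates instead of importing the SVR model as 8.3.2 does, so an analyst following it as written would omit them.
- The absence of an ITT adherence analysis is not itself a fault. SAP 3.3 explains that adherence is relevant only among initiators. It does mean that no fully randomised comparison is planned as a check.
- Copying the SVR rule is only a partial remedy (step 5).

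**Conclusion.** The textual discrepancy is certain: the adherence model in SAP 8.4.2 is narrower than SAP 5.4, SAP 8.3.2 and Protocol 11.10 on the same samples, and no reason is given. The statistical consequence is possible confounding of unknown size. Under the assumed correlations and selection models above, it ranges from negligible (0.009 SD, error near 5%) to material (0.08 SD or more, error near 30% or higher). The upper end depends on selection acting mainly in DOT, or on strong correlations with both initiation and adherence. The primary SVR analysis is not affected. The correction should be made because it is cheap and its rule is already in the SAP.

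**What to change.** In SAP 8.4.2, state that the mITT and PP adherence models adjust for the stratification variables plus the baseline characteristics found unbalanced under the SAP 5.4 rule, in line with Protocol 11.10. Say that this covers blister-pack adherence, and self-report when it is analysed.

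Extend the propensity-score or inverse-probability-weighting option of SAP 5.4 to adherence as a sensitivity analysis, because the p<0.01 screen misses smaller imbalances. Neither step deals with unmeasured factors, and the report should say so.

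The cost is a sentence or two in the SAP and the slight loss of precision in step 6. The baseline characteristics are already listed in SAP Table 1, so no new data are needed.
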